**Drug induced liver injury:**

Although rare, a potential for drug-induced liver injury (DILI) is under constant surveillance by sponsors and regulators. Therefore, this trial requires timely detection, evaluation, and follow-up of laboratory alterations in selected liver laboratory parameters to ensure subjects' safety; see also [Section 5.2.6.1.4](#), adverse events of special interest.

**1.4.3      Overall statement**

In summary, although not therapeutically tested in humans to date, BI 1358894 has the potential to become an oral treatment for major depressive disorder as an adjunct to antidepressant therapy and for the treatment of borderline personality disorder. Based upon preclinical data for BI 1358894, the clinical data from the on-going FIH study, as well as the implemented safety measures described above, healthy subjects will not be exposed to undue risks in relation to the important information expected from this trial as a basis for further clinical development of this compound. Healthy volunteers are not expected to have any direct benefit from participation in the clinical trial with BI 1358894, as is the usual case in such Phase I trials. Considering the medical need for the development of a safer and more effective treatment for patients with mood and borderline personality disorders, the Sponsor considers that the benefit outweighs the potential risks and justifies exposure of healthy human volunteers.

## **2. TRIAL OBJECTIVES AND ENDPOINTS**

### **2.1 MAIN OBJECTIVES, PRIMARY AND SECONDARY ENDPOINTS**

#### **2.1.1 Main objectives**

The main objective of this trial is to investigate the relative bioavailability of a single dose of 100 mg BI 1358894 administered as the tablet formulation 2 (TF2) conventional and TF2 non-conventional under fasted conditions compared with the tablet formulation 1 (TF1) of 100 mg of BI 1358894 under fed conditions following oral administration. In addition, this trial will investigate the food effect on the exposure of BI 1358894 with TF2 conventional and TF2 non-conventional.

#### **2.1.2 Primary endpoints**

The following pharmacokinetic parameters will be determined for BI 1358894:

- $C_{\max}$  (maximum measured concentration of the analyte in plasma)
- $AUC_{0-tz}$  (area under the concentration-time curve of the analyte in plasma over the time interval from 0 to the last quantifiable data point)

#### **2.1.3 Secondary endpoints**

The following pharmacokinetic parameters will be determined for BI 1358894:

- $AUC_{0-\infty}$  (area under the concentration-time curve of the analyte in plasma over the time interval from 0 extrapolated to infinity)
- $AUC_{0-72}$  (area under the concentration-time curve of the analyte in plasma over the time interval from 0 to 72 h)

Proprietary confidential information © 2019 Boehringer Ingelheim International GmbH or one or more of its affiliated companies

### 3. DESCRIPTION OF DESIGN AND TRIAL POPULATION

#### 3.1 OVERALL TRIAL DESIGN AND PLAN

The study will be performed as a randomised, open-label, single-dose, incomplete blocks crossover trial in healthy male subjects in order to compare the test treatments TF2 in fasted state (C and E) to the reference treatment TF1 in fed state (A) to investigate the relative bioavailability of tablet formulation. Additionally, it will evaluate the food effect on test treatments. The test treatments will be one single dose of 100 mg BI 1358894 of the TF2 in a fed state (B) and in the fasted state (C) and TF2 in the fed state (D) and in the fasted state (E). The reference treatment to compare the bioavailability of tablet formulations will be one single dose of 100 mg BI 1358894 of the TF1 (A) administered to subjects in the fed state.

Twenty-four subjects will be randomly allocated to 12 treatment sequences. For details, refer to [Section 4.1](#).

The planned 24 subjects to be included in the study will be assigned to three cohorts, each consisting of eight subjects. The cohorts will be treated at least one week apart. The second and third cohort will be dosed after a careful review by the Investigator of the safety data from all subjects in the preceding cohort(s).

Table 3.1: Treatment sequences

Blocks/Sequences	1	2	3	4	5	6	7	8	9	10	11	12
Period 1	A	D	E	C	A	E	B	C	B	D	C	A
Period 2	B	A	B	A	E	D	C	E	D	C	B	E
Period 3	C	B	A	D	C	A	D	B	E	E	A	D

There will be a washout period of at least 17 days between the treatments, i.e. the dose in the first treatment period and the dose in the second treatment period are separated by at least 17 days. In each subject, an assessment of safety laboratory, vital signs, ECG and AEs will be conducted on the last day of the preceding period prior to next dosing. These data will be reviewed by the Investigator to confirm the eligibility of the subject before the following dosing.

An overview of all relevant trial activities is provided in the [Flow Chart](#). For visit schedule and details of trial procedures at selected visits, refer to [Sections 6.1](#) and [6.2](#), respectively.

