#### **4.1.3 Method of assigning subjects to treatment groups**

The randomisation list will be provided to the trial site in advance.

Subjects will be allocated to treatment sequences prior to the first administration of trial medication in the morning of Day 1 (Visit 2). For this purpose, numbers of the randomisation list will be allocated to the subjects by the method first come first served. Subjects are then assigned to a treatment sequence according to the randomisation list.

Proprietary confidential information © 2019 Boehringer Ingelheim International GmbH or one or more of its affiliated companies

Within the treatment sequence, numbers of the randomisation list will be allocated to subjects in their order of registration for the study (that is, the first subject registered will be the first treated and will receive the first number of the respective treatment sequence in the randomisation list).

Once a subject number has been assigned, it cannot be reassigned to any other subject.

The randomisation procedure is described in [Section 7.6](#).

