#### **7.6 RANDOMISATION**

Subjects will be randomised to one of the 12 treatment sequences in a 1:1:1:1:1:1:1:1:1:1:1:1 ratio. The block size will be documented in the CTR.

The sponsor will arrange for the randomisation as well as packaging and labelling of trial medication. The randomisation list will be generated using a validated system that uses a pseudo-random number generator and a supplied seed number so that the resulting allocation is both reproducible and non-predictable.

The randomisation list will contain additional blocks to allow for subject replacement (refer to [Section 3.3.5](#)).

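### If cohort 2 is released before cohort 1's second dose, there is a 28% to 51% chance (block size 12 or 24) that at least one TF2 formulation-by-food treatment has not yet been given when the safety review takes place

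*Protocol*

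**What the plan says.** Protocol Section 3.1 states that the 24 subjects "will be assigned to three cohorts, each consisting of eight subjects". On spacing it says: "The cohorts will be treated at least one week apart". The release rule is: "The second and third cohort will be dosed after a careful review by the Investigator of the safety data from all subjects" of earlier cohorts. It does not say which periods that review must include or which treatments must be represented.

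Section 3.1 also says that "the dose in the first treatment period and the dose in the second treatment period are separated by at least 17 days". The first row of Table 3.1 reads "Period 1 A D E C A E B C B D C A" for sequences 1 to 12.

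Section 7.6 says: "Subjects will be randomised to one of the 12 treatment sequences in a 1:1:1:1:1:1:1:1:1:1:1:1 ratio". It leaves the block size to be documented in the trial report. Section 4.1.3 adds that "numbers of the randomisation list will be allocated to the subjects by the method first come first served". Neither section mentions cohorts.

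**The concern.** Staggered cohorts exist so that early subjects can inform the release of later ones. For a given treatment, that works only if someone in the earlier cohort has received it. Eight is not a multiple of 12, so a list balanced over 12 sequences cannot be balanced within a cohort of eight unless it is restricted to be so. Table 3.1 starts only two sequences each with B, D and E.

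Food state matters as well as product. In the first-in-human trial, 100 mg of TF1 gave fed/fasted ratios of 2.46 for Cmax and 2.88 for AUC0-24 (Table 1.2.1.5: 5). Whether TF2 removes that food effect is one of this trial's questions, so fasted data on a TF2 product do not simply stand in for fed data. The risk-minimisation text in Section 1.4.2 rests on experience from the first-in-human trial, which used TF1. Section 1.3 says that the newer formulations were sought for higher fasted exposure.

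**Working it through.** **Plan's own figure.** 3 cohorts x 8 = 24, and 12 sequences x 2 = 24; these agree. The plan gives no probability for treatment coverage by cohort.

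**Inputs**
- Period 1 starts over the 12 sequences (Table 3.1): A 3, B 2, C 3, D 2, E 2. Over 24 places these double to A 6, B 4, C 6, D 4, E 4.
- Cohort 1 takes the first 8 numbers on the list (Sections 3.1 and 4.1.3).
- Block size: not stated. Assumed to be 12 or 24, the sizes that give exactly two subjects per sequence in 24.
- Timing: cohorts at least 7 days apart, doses within a subject at least 17 days apart. If cohort 2 starts 7 to 16 days after cohort 1, only Period 1 doses exist. At exactly one-week steps cohort 3 starts 14 days after cohort 1, still before any second dose.

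**Formula.** If k list places do not start with any treatment in a given set, P(set absent from cohort 1) = C(k,8)/C(N,8), with N = 12 or 24. Inclusion-exclusion over B, C, D and E gives the chance that at least one is absent.

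**Block 12**, C(12,8) = 495:
- B, D or E absent: C(10,8) = 45 each, or 9.1%. C absent: C(9,8) = 9, or 1.8%.
- Pairs BD, BE, DE: C(8,8) = 1 each. Pairs with C, and all larger sets: 0.
- At least one absent: (3 x 45 + 9 - 3)/495 = 141/495 = **28.5%**. Enumerating all 495 subsets also gives 141.

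**Block 24**, C(24,8) = 735,471:
- B, D or E absent: C(20,8) = 125,970 each, or 17.1%. C absent: C(18,8) = 43,758, or 5.9%.
- Pairs: 3 x C(16,8) + 3 x C(14,8) = 3 x 12,870 + 3 x 3,003 = 47,619.
- Triples: C(12,8) + 3 x C(10,8) = 495 + 135 = 630. All four: 0.
- At least one absent: (3 x 125,970 + 43,758 - 47,619 + 630)/735,471 = 374,679/735,471 = **50.9%**. A simulation of 400,000 draws agrees.

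**TF2 fed treatments only (B or D absent):** (45 + 45 - 1)/495 = 18.0%, or (2 x 125,970 - 12,870)/735,471 = 32.5%.

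**How the result depends on timing and on what counts as absent**

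| Quantity for cohort 1 | Block 12 | Block 24 |
|---|---|---|
| At least one of B, C, D, E absent, Period 1 only | 28.5% | 50.9% |
| Same, after two doses | 0.2% | 3.0% |
| Same, after all three doses | 0% | 0.02% |
| A whole TF2 product absent (B and C, or D and E), Period 1 only | 0.2% | 2.2% |

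**How many cohort 2 subjects are affected.** B, D and E have four Period 1 places each in the whole trial and C has six, so at most 4 (6 for C) cohort 2 subjects can start on the absent treatment. If B, D or E is absent from cohort 1, the expected number is 2 + 2 x 4/12 = 2.7 (block 12) or 4 x 8/16 = 2.0 (block 24).

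**The case against.** The strongest reply is about timing. One week is a floor, and the release rule is a separate condition that Section 3.1 does not limit to Period 1. If the review waited for cohort 1's second dose, the chance would nearly vanish. This stands: 28-51% is conditional on early release, and a reader who took it as the trial's overall chance would go beyond the documents. Still, one week is the only spacing given, and the summary of Amendment 1 in Section 11.1 also describes a one-week separation.

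The block size is likewise an assumption, and the randomisation list is not available to check. The list may have been built by cohort although the protocol does not say so.

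A reader might also infer that a new tablet could be wholly untested at the review. Table 3.1 does not support that: in nearly all cases the same product has been given in the other food state. Nor could all eight cohort 2 subjects start on the missing treatment, because Table 3.1 has too few Period 1 places.

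Other protections do not depend on cohort composition: 72 hours of in-house observation, review before each subject's next dose, and trial-level discontinuation criteria. The drug and the 100 mg dose are not new either. TF1 fed at 100 mg gave a Cmax of 517 nmol/L against a threshold of 1960 nM (1960/517 = 3.8-fold), and 200 mg fasted was well tolerated. TF2 exposure is unmeasured, but these facts limit the stakes.

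Finally, one subject per treatment is little evidence: an event with a 10% rate would be seen in that subject only 10% of the time. That also stands, and it limits what the fix can achieve.

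**Conclusion.** The gap is real but conditional. If cohort 2 starts 7 to 16 days after cohort 1, which the protocol permits, and the list is used in order with block size 12 or 24, the review that releases cohort 2 has a 28% to 51% chance of containing no subject on at least one of B, C, D and E.

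It would be wrong to conclude that the staggering is ineffective, that a TF2 product is likely to go unobserved, or that the documents contradict one another. No endpoint, estimate or analysis is affected. This is an inexpensive improvement to how the list is built, with a modest safety benefit.

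**What to change.** In Sections 7.6 and 4.1.3, generate the list in three cohort blocks of eight drawn from the same 24 places (each sequence twice), restricted so that every treatment appears in Period 1 of each cohort. One split that works:

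| Period 1 treatment | Cohort 1 | Cohort 2 | Cohort 3 | Total |
|---|---|---|---|---|
| A | 2 | 2 | 2 | 6 |
| B | 2 | 1 | 1 | 4 |
| C | 2 | 2 | 2 | 6 |
| D | 1 | 2 | 1 | 4 |
| E | 1 | 1 | 2 | 4 |
| Sum | 8 | 8 | 8 | 24 |

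Replacements keep the sequence of the subject replaced, as Section 3.3.5 already provides. The 1:1 ratio and the analysis do not change. The cost is that the last allocations within a cohort become slightly more predictable, which matters little in an open-label trial whose bioanalytical laboratory is blinded. The restriction ensures that each review covers every formulation and food state at least once, even at the one-week minimum.

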#### 3.2 DISCUSSION OF TRIAL DESIGN, INCLUDING THE CHOICE OF CONTROL GROUPS

For relative bioavailability trials, the crossover design is preferred because of its efficiency: since each subject serves as his own control, the comparison between formulations is based on an intra-subject comparison, thus removing inter-subject variability from the comparison between formulations [[R94-1529](#)]. The incomplete blocks design was chosen for this study

Proprietary confidential information © 2019 Boehringer Ingelheim International GmbH or one or more of its affiliated companies

instead of a full 5x5 crossover design due to the long apparent terminal half-life of BI 1358894 (between 54.8 and 82.5 h) resulting in a long washout period (17 days).

The open-label treatment is not expected to bias results, since the study endpoints are derived from measurement of plasma concentrations of BI 1358894, which are provided by a bioanalytical laboratory that is blinded to treatment allocation.

### **3.3 SELECTION OF TRIAL POPULATION**

It is planned that 24 healthy male subjects will enter the study. They will be recruited from the volunteers' pool of the trial site.

Only healthy male subjects will be included in the study which is a standard population in early clinical development.

A log of all subjects enrolled into the trial (i.e. who have signed informed consent) will be maintained in the ISF irrespective of whether they have been treated with investigational drug or not.

#### **3.3.1 Main diagnosis for trial entry**

The study will be performed in healthy subjects.

#### **3.3.2 Inclusion criteria**

Subjects will only be included in the trial if they meet the following criteria:

1. Healthy male subjects according to the assessment of the investigator, as based on a complete medical history including a physical examination, vital signs (BP, PR), 12-lead ECG, and clinical laboratory tests.
2. Age of 18 to 50 years (inclusive)
3. BMI of 18.5 to 29.9 kg/m^2 (inclusive)
4. Signed and dated written informed consent prior to admission to the study, in accordance with GCP and local legislation

Proprietary confidential information © 2019 Boehringer Ingelheim International GmbH or one or more of its affiliated companies

5. Male subjects who meet any of the following criteria from at least 30 days before the first administration of trial medication until 30 days after trial completion:
  - Use of adequate contraception of the female partner, e.g. any of the following methods *plus* condom: implants, injectables, combined oral or vaginal contraceptives, intrauterine device (IUD) that started at least 2 months prior to first study drug administration, or barrier method (e.g. diaphragm with spermicide)
  - Sexually abstinent
  - A vasectomy performed at least 1 year prior to screening (with medical assessment of the surgical success)
  - Surgically sterilised female partner (including hysterectomy, bilateral tubal occlusion or bilateral oophorectomy)

### **3.3.3 Exclusion criteria**

Subjects will not be allowed to participate, if any of the following general criteria apply:

1. Any finding in the medical examination (including BP, PR or ECG) deviating from normal and assessed as clinically relevant by the investigator
2. Repeated measurement of systolic blood pressure outside the range of 90 to 140 mmHg, diastolic blood pressure outside the range of 50 to 90 mmHg, or pulse rate outside the range of 50 to 90 bpm
3. C-Reactive Protein (CRP) > upper limit of normal (ULN), erythrocyte sedimentation rate (ESR)  $\geq$ 15 millimeters/h, liver or kidney parameter above ULN, or any other laboratory value outside the reference range that the investigator considers to be of clinical relevance
4. Any evidence of a concomitant disease assessed as clinically relevant by the investigator
5. Gastrointestinal, hepatic, renal, respiratory, cardiovascular, metabolic, immunological or hormonal disorders
6. Cholecystectomy or other surgery of the gastrointestinal tract that could interfere with the pharmacokinetics of the trial medication (except appendectomy and simple hernia repair)
7. Diseases of the central nervous system (including but not limited to any kind of seizures or stroke), and other relevant neurological or psychiatric disorders
8. History of relevant orthostatic hypotension, fainting spells, or blackouts
9. Chronic or relevant acute infections
10. History of relevant allergy or hypersensitivity (including allergy to the trial medication or its excipients) (Lists of excipients are provided in the Investigator's Brochure Section 4.2 for Tablet Formulation 1 and in Appendix 10.2 for Tablet Formulation 2 conventional and Tablet Formulation 2 non-conventional.)
11. Use of drugs within 30 days of planned administration of trial medication that might reasonably influence the results of the trial (including drugs that cause QT/QTc interval prolongation)
12. Intake of an investigational drug in another clinical trial within 60 days of planned administration of investigational drug in the current trial, or concurrent participation in another clinical trial in which investigational drug is administered
13. Smoker (more than 10 cigarettes or 3 cigars or 3 pipes per day)

Proprietary confidential information © 2019 Boehringer Ingelheim International GmbH or one or more of its affiliated companies

14. Inability to refrain from smoking on specified trial days
15. Alcohol abuse (consumption of more than 30 g per day)
16. Drug abuse or positive drug screening
17. Blood donation of more than 100 mL within 30 days of planned administration of trial medication or intended blood donation during the trial
18. Intention to perform excessive physical activities within one week prior to the administration of trial medication or during the trial
19. Inability to comply with the dietary regimen of the trial site
20. A marked baseline prolongation of QT/QTc interval (such as QTc intervals that are repeatedly greater than 450 ms) or any other relevant ECG finding at screening
21. A history of additional risk factors for *Torsade de Pointes* (such as heart failure, hypokalaemia, or family history of Long QT Syndrome)
22. Subject is assessed as unsuitable for inclusion by the investigator, for instance, because the subject is not considered able to understand and comply with study requirements, or has a condition that would not allow safe participation in the study

In addition, the following trial-specific exclusion criteria apply:

23. Any lifetime history of suicidal behaviour (i.e. actual attempt, interrupted attempt, aborted attempt, or preparatory acts or behaviour)
24. Any suicidal ideation of type 2 to 5 on the C-SSRS in the past 12 months (i.e. active suicidal thought, active suicidal thought with method, active suicidal thought with intent but without specific plan, or active suicidal thought with plan and intent)

For study restrictions, refer to [Section 4.2.2](#).

### 3.3.4 Withdrawal of subjects from treatment or assessments

Subjects may discontinue trial treatment or withdraw consent to trial participation as a whole ('withdrawal of consent') with very different implications; please see [Sections 3.3.4.1](#) and [3.3.4.2](#) below.

If a subject is removed from or withdraws from the trial prior to the first administration of trial medication, the data of this subject will not be entered in the case report form (CRF) and will not be reported in the clinical trial report (CTR). If a subject is removed from or withdraws from the trial after the first administration of trial medication, this will be documented and the reason for discontinuation must be recorded in the CRF; in addition, the data will be included in the CRF and will be reported in the CTR. At the time of discontinuation, a complete end of trial examination will be performed, if possible, and the information will be recorded in the CRF. If the discontinuation occurs before the end of the REP (see [Section 1.2.2](#)), the discontinued subject should if possible be questioned for AEs and concomitant therapies at or after the end of the REP in order to ensure collection of AEs and concomitant therapies throughout the REP, if not contrary to any consent withdrawal of the subject.

### 3.3.4.1 Discontinuation of trial treatment

An individual subject will discontinue trial treatment if:

1. The subject wants to discontinue trial treatment or trial participation, without the need to justify the decision
2. The subject has repeatedly shown to be non-compliant with important trial procedures and, in the opinion of both, the investigator and sponsor representative, is not willing or able to adhere to the trial requirements in the future.
3. The subject needs to take concomitant medication that interferes with the investigational medicinal product or other trial treatment
4. The subject can no longer receive trial treatment for medical reasons (such as surgery, adverse events [AEs], or diseases)
5. The subject shows a raised CRP level of  $>3.00$  mg/dL or an ESR of  $\geq 20$  millimetres/hour
6. An AE or clinically significant laboratory change or abnormality occurred that the investigator judges to warrant discontinuation of treatment. This may include cases of sustained symptomatic hypotension (BP $<90/50$  mmHg) or hypertension (BP $>180/100$  mmHg) or of clinically relevant changes in ECG requiring intervention as well as unexplained liver enzyme elevations at any time during the trial.
7. The subject has an elevation of AST and/or ALT  $\geq 3$ -fold ULN and an elevation of total bilirubin  $\geq 2$ -fold ULN (measured in the same blood sample) and/or needs to be followed up according to the DILI checklist provided in the ISF
8. The subject experiences a serious adverse reaction which is considered at least possibly related to the IMP administration

In addition to these criteria, the investigator may discontinue subjects at any time based on his or her clinical judgment.

Even if the trial treatment is discontinued, the subject remains in the trial and, given his/her agreement, will undergo the procedures for early treatment discontinuation and follow up as outlined in the [Flow Chart](#) and [Section 6.2.3](#).

